With the FDA approval of Impella (Abiomed, Danvers, MA) in AMICS, a powerful new tool has become available for hemodynamic support. Impella is a transcatheter axial flow pump, delivered percutaneous, with the ability to provide 2.5 to 4.0 liters/minute of forward flow. The device should provide sufficient forward cardiac flow to support vital organs in the majority of patients who present with AMICS. Since Impella is the only percutaneous temporary ventricular support device approved as safe and effective for use in AMICS, the use of the device has steadily grown⁸. Unfortunately, there is little data available to providers as to the best practice patterns associated with the delivery and use of Impella in AMICS. In fact, a retrospective analysis of 15,259 patients treated with an Impella between 2009 and 2017 revealed a wide variety of outcomes associated with the use of Impella in AMICS, with approximately one third of hospitals having a survival rate of 25%, another third of hospitals having a survival rate of 50%, and yet another third of hospitals having a survival rate of 75%.

In the summer of 2016, cardiologists from four highly competitive healthcare systems in southeast Michigan came together in an attempt to increase survival in patients who present with

AMICS. Leaders from each healthcare system debated and discussed key elements in the improvement of care for patients who present with AMICS. Using the most up-to-date research, a treatment algorithm for AMICS was developed and subsequently implemented as a quality improvement initiative throughout southeast Michigan. Patient information was gathered by each of the sites and collected in a retrospective registry. Outcomes and results were shared during quarterly meetings and concluded with a 41-patient pilot feasibility study. This initial pilot study revealed a 76% survival to discharge, a significant improvement compared to prior historical controls⁹.

Given the promising outcomes, leaders from around the world have implemented the treatment algorithm in their local clinical practices with similar results. We have therefore launched the National Cardiogenic Shock Initiative (NCSI). The aim of the NCSI is to bring together experienced centers across the nation who are experts in mechanical reperfusion therapies and have a large experience with the use of mechanical circulatory support devices to systematize care in AMICS. Our goal is to dramatically decrease the duration patients remain in cardiogenic shock and attempt to decrease total usage and duration of vasopressors and inotropic agents. We aim to further demonstrate that rapid delivery of mechanical circulatory support will improve hemodynamics, reverse the spiraling neuro-hormonal cascade associated with cardiogenic shock, allowing clinicians to decrease use of vasopressors and inotropic agents and ultimately improve survival.

Healthcare systems that have agreed to adopt the NCSI treatment algorithm are being asked to participate in this prospective registry so that patient outcomes can be analyzed (see Appendix 2). Participating investigators will be asked to voluntarily provide data from patients completing the treatment algorithm to be included in the NCSI Registry.

Research Procedures

After a patient has been treated according to the NCSI treatment algorithm at the discretion of their physician (see Appendix 1), they will be approached prior to discharge and asked to participate in NCSI registry, including obtaining permission to allowing coordinators to conduct a 1-month and 1-year follow-up. This data collection can occur via follow up phone call, electronic chart review, or any other method that complies with the site's SOPs. If the patient is discharged prior to obtaining consent, consent form and explanation of the study can be mailed to the patient for their signature and return. If more than one (1) year has passed, all data may be obtained retrospectively.

If consent is provided, then the following data will be collected (see case report form - Appendix 3):

Retrospective Data (from their medical records)

- Medical history
- Admission characteristics
- Procedure dates and times
- Procedure characteristics
- Diagnostic values
- Post-procedure information

Prospective Data (from follow-up) (see Appendix 5 and Appendix 6)

- Mortality at 1 month from AMICS
- Mortality at 12 months from AMICS

From this data, the following Quality Metrics will be tracked:

- Discharge survival
- Duration of shock-to-support times

- Use of Impella Support pre-PCI
- Use of right heart catheter for hemodynamic monitoring
- Attainment of TIMI III flow post reperfusion
- Attainment of Cardiac power > 0.6 watts after completion of therapy
- Reduction or elimination of vasopressors and inotropic agents.

Population and Eligibility Criteria

Due to the heterogeneous cohort of patients who present with AMICS, we have defined a specific subset of patients from whom outcomes are to be collected. Approximately 500 adult patients will be approached to participate in the registry at approximately 75 sites in the United States. The duration of hospital participation in this research study is anticipated to be approximately 3 years.

Registry Inclusion Criteria

1. Symptoms of acute myocardial infarction (AMI) with ECG and/or biomarker evidence of S-T elevation myocardial infarction (STEMI) or non-S-T elevation myocardial infarction (NSTEMI)
2. Cardiogenic shock is defined as the presence of at least two of the following:
 - a. Hypotension (systolic blood pressure ≤ 90 mm Hg, or inotropes/vasopressors to maintain systolic blood pressure ≥ 90 mmHg)
 - b. Signs of end organ hypoperfusion (cool extremities, oliguria or anuria, or elevated lactate levels)
 - c. Hemodynamic criteria represented by a cardiac index of < 2.2 L/min/m² or a cardiac power output ≤ 0.6 watts.

3. Patient is supported with an Impella
4. Patient undergoes PCI

Registry Exclusion Criteria

1. Evidence of Anoxic Brain Injury
2. Unwitnessed out of hospital cardiac arrest or any cardiac arrest in which return of spontaneous circulation (ROSC) is not achieved within 30 minutes
3. IABP placed prior to Impella
4. Septic, anaphylactic, hemorrhagic, and neurologic causes of shock
5. Non-ischemic causes of shock/hypotension (pulmonary embolism, pneumothorax, myocarditis, tamponade, etc.)
6. Active bleeding for which mechanical circulatory support is contraindicated
7. Recent major surgery for which mechanical circulatory support is contraindicated
8. Mechanical complications of AMI (acute ventricular septal defect (VSD) or acute papillary muscle rupture)
9. Known left ventricular thrombus for which mechanical circulatory support is contraindicated
10. Mechanical aortic prosthetic valve
11. Contraindication to intravenous systemic anticoagulation

Risks/Benefits of and Alternatives to Patient Participation

This is not a treatment study. This is a single-arm prospective registry that captures data generated during procedures which are considered standard of care using FDA-approved technology. There are no risks other than breach of confidentiality. To mitigate this risk, patient identifiers are not being captured, and all data will be stored in a secure REDCap database

(please see below). There are no benefits in participation other than the scientific knowledge gained, and the only alternative to participation is not participating.

Data Management

Data collected by the participating sites will be stored and managed in a secure REDCap study database hosted through the Henry Ford Health System Department of Public Health Sciences in Detroit, Michigan. REDCap (Research Electronic Data Capture) is a secure, web-based application designed to support data capture for research studies. A specific database was created solely for NCSI in September 2017. The REDCap database that was custom-built for this study includes only the specific data fields that pertain to the data points being collected in the study, which are present on the case report form (CRF) (see Appendix 3).

For patients who present to affiliated hospitals with AMICGS but are excluded from entry into the registry, a Patient Exclusion Form will be sent to track the reasons for exclusion (see Appendix 4).

The CRFs and Patient Exclusion Forms from an individual site will be transmitted to the lead site, Henry Ford Hospital, via secure email and accessed only on hospital-approved, password-protected computers and stored on a password-protected and encrypted OneDrive system by Microsoft. Access to the OneDrive system and the REDCap database will be managed at the lead site by the NCSI coordinator and the investigators of the study via hospital-approved, password-protected computers inside locked offices in Henry Ford Hospital.

Access to Patient Information

The following will have access to the de-identified patient medical information, and any necessary research contracts and Data Use Agreements will be completed for each participating site.

Henry Ford Hospital – Detroit, Michigan:

- The NCSI team:
 - PI
 - Co-Investigator
 - NCSI Coordinator
 - Research Nurse
 - Research Assistant
 - Data Coordinator
- Statistician, based at Henry Ford Hospital

Analysis and Publication of Data

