Prior to discharge from the cath lab, a formal neurovascular check should be performed for assessment of Impella-related limb ischemia. This can be performed either by an in-depth physical examination, peripheral angiogram, or lower extremities doppler studies. If signs of limb ischemia are noted, the peel-away sheath should be removed (if not already done so) with reassessment. If limb ischemia persists, antegrade access should be performed to provide distal lower extremity blood flow.

4. Post-PCI Hemodynamics

After the intervention is completed, right heart pressures, cardiac output, and CPO will be obtained. If CPO is > 0.6 , no further intervention is required. If CPO is ≤ 0.6 , right heart pressure will be reviewed to identify evidence of right ventricular failure if present (PAPi < 0.9).

If evidence of right ventricular failure are present (PAPi < 0.9), or if the Impella is suctioning, operators should consider right ventricular support with commercially available devices (Impella or Tandem Heart). Irrespective of CPO, evidence of RV shock is a warning not

to increase alpha agonists. These agents dramatically increase pulmonary vascular resistance (PVR) at a time of minimal RV reserve and can cause a lethal spiral as increasing doses of alpha agonists to maintain arterial pressure leads to decrease forward RV flow and worsens hypotension.

If CPO < 0.6 persists and RV shock is not the cause, consideration for the placement of an Impella 5.0 or a durable left ventricular assist device (LVAD) should be considered.

5. Weaning and Explantation

Impella devices should only be considered for explantation once the following criteria have been met:

1. Weaning of all inotropes and vasopressors
2. CPO > 0.6 watts without vasopressors or inotropes, and
3. PAPI > 0.9.

6. Safety and Monitoring

Cautious attention should be paid to the infrequent yet serious complication of limb ischemia with the use of large bore sheaths and devices. Detailed neurovascular checks should be performed while on Impella support. Use of antegrade sheaths to provide flow to the affected limb is strongly recommended in such cases. Prophylactic use antegrade access may also be considered, especially in patients who will likely require >24 hours of support. Although rare hemolysis can also occur, daily hemoglobin level should be obtained while on support. If there are signs of hematuria, Impella positioning should be checked via echocardiography.

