** QUALITY MEASURES **

- Impella Pre-PCI
- Door to Support Time < 90 minutes
- Establish TIMI III Flow
- Right Heart Cath
- Wean off Vasopressors & Inotropes
- Maintain CPO >0.6 Watts
- Improve survival to discharge to >80%

NATIONAL CARDIOGENIC SHOCK INITIATIVE

[contact]

www.henryford.com/cardiogenicshock

NationalCSI - Algorithm - v1.5 - 11/2017

APPENDIX 2

Adoption of the NCSI Treatment Algorithm & Joining the NCSI

Adoption to the NCSI treatment algorithm is completely voluntary. Deviation from the treatment algorithm can occur without consultation of the primary investigators at the discretion of the primary operator. All AMICS patients, including those with treatment algorithm deviation, can be included in the NCSI registry as there is no formal, nationally accepted or standardized protocol or treatment algorithm for treatment of AMICS. Operators and hospitals are encouraged to review the pilot study data and treatment algorithm to determine if they wish to adopt the NCSI treatment algorithm as their standard of care for the treatment of AMICS.

Multi-hospital collaboration is considered a cornerstone to the success of the NCSI. We are reaching out nationally and encouraging hospitals to work together to collect data and demonstrate the success of regional shock protocols and/or treatment algorithms. Hospitals joining the NCSI group voluntarily agree to share data, post-discharge, including demographics, procedural characteristics and outcomes as detailed in the case report form. Data is de-identified and HIPAA-compliant. Data generated from the index procedure admission to discharge (or death, if prior to discharge) will be collected retrospectively and de-identified. Prior to discharge, surviving patients will be asked to consent to the collection of data at 30 days and 1 year post-index procedure. This data collection can occur via follow up phone call, electronic chart review, or any other method that complies with the site's SOPs.

To formally join and affiliate with NCSI, we request the minimum following requirements of the interested hospitals:

1. Implantation of >10 Impella per year (for any indication)

2. Adoption of the NCSI treatment algorithm as standard of care for patients who present with AMICS
3. Identification of a local Primary Investigator (PI) to coordinate data collection

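### The protocol gives conflicting entry rules on algorithm adherence, so a site can comply while leaving out deviating patients, which can inflate the process metrics and discharge survival

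*Protocol*

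**What the plan says.** Three places in the protocol bear on who enters the registry.

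- **Introduction and Research Procedures.** The paragraph just before Research Procedures asks investigators to "voluntarily provide data from patients completing the treatment algorithm to be included in the NCSI Registry". Research Procedures then describes the approach for consent: "After a patient has been treated according to the NCSI treatment algorithm at the discretion of their physician", the patient is asked to take part.
- **Appendix 2.** "Deviation from the treatment algorithm can occur without consultation of the primary investigators at the discretion of the primary operator". It continues: "All AMICS patients, including those with treatment algorithm deviation, can be included in the NCSI registry". It also says that joining hospitals share data after discharge.
- **Population and Eligibility Criteria.** The inclusion list asks for AMI, shock, Impella support ("Patient is supported with an Impella") and PCI, followed by 11 exclusions. Neither following nor completing the algorithm is a criterion.

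Under the lead-in "From this data, the following Quality Metrics will be tracked", the protocol lists discharge survival, shock-to-support time, Impella before PCI, "Use of right heart catheter for hemodynamic monitoring", TIMI III flow, cardiac power above 0.6 watts, and reduction or elimination of vasopressors and inotropes. Apart from discharge survival, these are largely steps or targets of the algorithm in Appendix 1. For example, one of its explantation conditions is "CPO > 0.6 watts without vasopressors or inotropes, and" a PAPI threshold.

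**The concern.** If entry depends on having followed the algorithm, a metric that counts how often an algorithm step was done partly measures the entry rule and not the site's practice. If the omitted patients also die more often, discharge survival is overstated. The registry has a single arm, so the interpretation of its survival figure rests on which patients are in the denominator.

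The conflict lies in the entry rule itself. An analysis plan cannot recover cases that were never sent, so the point has to be settled in the protocol.

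**Working it through.** **Comparing the passages**

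1. Under the introduction, a site that sends only patients who completed the algorithm is doing what it was asked.
2. Under Appendix 2, a site that also sends deviating patients is doing what it is allowed to do. The wording is permissive, and the introduction makes provision of data voluntary. No section requires consecutive or all-eligible entry.
3. Data are shared after discharge, so the outcome can be known when a case is submitted.
4. The Patient Exclusion Form (Appendix 4) is triggered by a failed inclusion item or a met exclusion item, including refusal of follow-up consent. It has no item for algorithm deviation or for an eligible case that was not sent. Such a patient leaves no record there.

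**Which metrics are exposed**

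- Right heart catheter use is the most direct. Appendix 1, section 2, says that the catheterization will be performed during the index procedure, so a patient treated according to the algorithm has had it.
- Impella before PCI is exposed to a lesser degree. The flowchart places Impella first, but Appendix 1, section 2, leaves the timing of mechanical support to the operator.
- TIMI III flow and cardiac power above 0.6 watts are targets. The algorithm says what to do when either is missed, so following it does not guarantee them.
- Discharge survival is exposed only if the omitted patients fare worse.

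**Illustration of size**

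The protocol gives no figure for this effect, so there is nothing to reproduce. Inputs:

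- s_c = 76%, survival of patients who follow the algorithm. This is the pilot's discharge survival, used here as an assumption.
- s_d = survival of deviating patients. Assumed at 50% or 25%, two of the hospital-level rates in the introduction, with 76% as the no-difference case.
- d = share of eligible patients who deviate. Assumed at 10% to 40%.
- q = share of deviating patients who are submitted. All others are submitted.

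Formulas:

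- Observed survival = [(1 − d)·s_c + q·d·s_d] / [(1 − d) + q·d]
- Observed adherence = (1 − d) / [(1 − d) + q·d]
- Overstatement = observed survival minus its value at q = 1

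With d = 20% and s_d = 50%:

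- All eligible patients (q = 1): 0.80 × 0.76 + 0.20 × 0.50 = 70.8% survival, 80% adherence.
- Half of deviating patients submitted (q = 0.5): (0.608 + 0.050) / 0.90 = 73.1% survival, 0.80 / 0.90 = 88.9% adherence.
- Completers only (q = 0): 76.0% survival, 100% adherence.

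Overstatement of survival in percentage points over the assumed range:

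| d | q = 0, s_d = 50% | q = 0, s_d = 25% | q = 0.5, s_d = 50% | q = 0.5, s_d = 25% |
|---|---|---|---|---|
| 10% | 2.6 | 5.1 | 1.2 | 2.4 |
| 20% | 5.2 | 10.2 | 2.3 | 4.5 |
| 30% | 7.8 | 15.3 | 3.2 | 6.3 |
| 40% | 10.4 | 20.4 | 3.9 | 7.7 |

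If s_d = 76%, the survival overstatement is 0 in every cell, but adherence is still overstated. For scale, the 95% half-width for 76% with 500 patients is 1.96 × √(0.76 × 0.24 / 500) = 3.7 points, so selection of this kind can exceed sampling error.

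**The case against.** The strongest reply is that the headed eligibility list is the entry rule and that the reference to completing the algorithm is loose wording. Much supports this. The list does not mention adherence. The introduction refers to Appendix 2 in the sentence just before the one at issue, and Appendix 2 admits deviating patients. The case report form has options for Impella after PCI, for no right heart catheterization, for post-PCI TIMI flow below 3 and for unsuccessful PCI. It also asks about survival of the index procedure and cause of death. Appendix 2 collects admission data up to discharge or death. A registry meant for completers only would not need these. This stands as evidence of intent, and it is why the bias is possible and not certain. It does not remove the conflict, because no text obliges a site to send the deviating case and no form shows that it was withheld.

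A reader might infer more: that the metrics are favourable by construction, with pre-PCI Impella and catheter use close to 100% by definition and early deaths dropped. The documents do not support that. The protocol does not define completion. The algorithm has branches for patients who do not recover (further support, transfer, palliative care), so a patient who dies on support has not plainly failed to complete it. The operator's discretion over timing weakens the claim for pre-PCI Impella.

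A reader might also remove deaths alone from the denominator. With 380 survivors among 500 (76%), omitting 25 of the 120 deaths gives 380/475 = 80.0%. The 25 has no source, leaving out only deaths maximises the effect, and 80.0% does not meet a goal set at above 80%.

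Finally, compulsory submission of every eligible case would clash with the protocol's consent provisions. That is right, and the fix allows for it.

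**Conclusion.** The protocol is wrong as written: its entry rules conflict, and this should be fixed. A site can comply while omitting deviating or non-completing patients. The process metrics can then be inflated, most directly right heart catheter use and to a lesser degree pre-PCI Impella. Discharge survival can be inflated if the omitted patients fare worse.

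The documents do not give the size. In the assumed central case, survival is overstated by 5.2 points and adherence by 20 points. The survival effect ranges from zero, if deviating patients fare the same, to 20.4 points at the extreme of the assumed range. All these figures rest on assumed deviation rates, submission rates and survival. They show what the wording permits and do not estimate what has happened.

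**What to change.** - In the introduction and in Research Procedures, replace the references to patients completing, or treated according to, the algorithm with: *all consecutive patients meeting the registry criteria, whether or not the algorithm was followed or completed*.
- In Appendix 2, change the permissive wording on patients with deviations so that all patients meeting the registry criteria *will be submitted, subject to the protocol's consent provisions*.
- Compute every quality metric on that full denominator, and report algorithm-adherent patients only as a subgroup.

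The cost is a wording amendment and a memo to sites. Sites will submit some additional cases, and reported adherence and survival may be slightly less favourable. The change concerns data entry only and alters nothing in patient care.

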| |  | Hypotension: Systolic blood pressure \leq 90mm at baseline, or use of inotropes or vasopressors to maintain SBP \geq 90 |
| |  | Evidence of end organ hypoperfusion (cool extremities, oliguria or anuria, or elevated lactate levels) |
| |  | Hemodynamic criteria: Cardiac index of $<$ 2.2 L/min/m ² or a cardiac power output \leq 0.6 watts. |
|  |  | Patient is supported with Impella |
|  |  | Patient undergoes PCI |

Continued on next page →

FOR HFH USE ONLY

NCSI #: _____

EXCLUSION CRITERIA:

YES NO

- Evidence of Anoxic Brain Injury
- Unwitnessed out of hospital cardiac arrest or any cardiac arrest in which ROSC is not achieved in 30 minutes
- IABP placed prior to Impella
- Septic, anaphylactic, hemorrhagic, and neurologic causes of shock
- Non-ischemic causes of shock/hypotension (*pulmonary embolism, pneumothorax, myocarditis, tamponade, etc.*)
- Active Bleeding
- Recent major surgery
- Mechanical Complications of AMI
- Known left ventricular thrombus
- Patient who did not receive revascularization
- Mechanical aortic valve
- Patient refused to sign consent for 1M & 1Y follow-up

Notes:

Completed by:

SIGNATURE

NAME (PRINTED)

DATE

APPENDIX 5
30 Day Follow-Up Form

National Cardiogenic Shock Initiative
30 Day Follow-Up
(Version 1.0)

Upon completion, please email this form via [SECURE] email to: [contact].
Please email/call if there are any questions or concerns.

NCSI #: _____

Hospital: _____

Hospital - City, State: _____

Date of Impella Implant: _____

Date of Follow-Up: _____

Patient Follow-Up – ≥ 30 Days from Date of Impella Implant:

Did the patient survive to 30 Days?

- YES
- NO
- Unknown
- Patient Unavailable
- Refused
- Other: _____

Point of Contact for Follow-up:

Patient Spouse LAR/Proxy Other: _____

Method of Follow-up:

- Phone Call
- Electronic Medical Record Review (patient signed-in for visit with ID at 30 or more days)
- Mail
- Email
- Other: _____

NOTES: _____

Follow-up performed by: _____

Title: _____

Signature: _____ Date: _____

APPENDIX 6
1 Year Follow-Up Form

National Cardiogenic Shock Initiative

1 Year Follow-Up

(Version 1.0)

Upon completion, please email this form via [SECURE] email to: [contact].
Please email/call if there are any questions or concerns.

NCSI #: _____

Hospital: _____

Hospital - City, State: _____

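### Mailed consent with no time limit, and retrospective entry after one year, lose post-discharge deaths that occur before entry, so mortality counted from implant comes out too low

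*Protocol*

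**What the plan says.** Research Procedures sets the normal route: after treatment, "they will be approached prior to discharge and asked to participate in NCSI registry". Two later routes follow.

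- **Mail.** If the patient has already left hospital, "consent form and explanation of the study can be mailed to the patient for their signature and return". No closing date is given.
- **Retrospective.** "If more than one (1) year has passed, all data may be obtained retrospectively". The text does not say when that year starts or whether consent is still needed.

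The same section lists mortality at 1 and 12 months as prospective data, counted from AMICS. Appendix 2 counts from the index procedure. Appendices 5 and 6 count from Impella implant; the first asks "Did the patient survive to 30 Days". The Risks/Benefits section states the design: "This is a single-arm prospective registry that captures data generated during procedures".

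The two accounts of consent differ. Research Procedures makes everything conditional: "If consent is provided, then the following data will be collected". Appendix 2 ties consent to follow-up alone: "Data generated from the index procedure admission to discharge (or death, if prior to discharge) will be collected retrospectively and de-identified", and then "Prior to discharge, surviving patients will be asked to consent to the collection of data at 30 days and 1 year post-index procedure".

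Neither the case report form (CRF, Appendix 3) nor the follow-up forms have a field for date of consent, route of entry or date of death. The Patient Exclusion Form (Appendix 4) has a box for refusing follow-up consent. It has none for death before consent or for a form not returned.

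**The concern.** The clock starts at implant, but a mailed-consent patient is observed only from signature. Between discharge and signature that patient must be alive in order to enter. This is immortal time: deaths in the interval drop out of numerator and denominator, while survivors of the interval stay in both. Anyone who signs after day 30 cannot be a 30-day death.

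The retrospective route has a related problem on either reading. If a signature is still needed, everyone entering this way has survived one year. If it is not, deaths can be captured, but a site can know the 1-year result when it decides whether to submit the patient. Sites submit data voluntarily, and the text has no consecutive-enrolment rule.

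The registry has one arm and aims to show better survival. No control group shares the loss of deaths, and on the mail route the error favours the conclusion sought.

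**Working it through.** The protocol gives no mortality estimate, sample-size calculation or share of late entrants to reproduce. The only figure available is the pilot's 76% survival to discharge in 41 patients (31/41 = 75.6%). All other inputs are assumptions.

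**Inputs**

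- S = 0.76, discharge survival (pilot, protocol background).
- m = 0.15, 1-year mortality after discharge alive (assumed; 0.10 and 0.25 also tried).
- e = m/2 = 0.075, the part of m falling by day 90 (assumed).
- L = 0.30 or 0.50, share of discharged patients entering by mail, all at day 90 (assumed). Everyone alive then returns the form.

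**Step 1: discharged patients.** Lost deaths are L × e of those discharged.

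Apparent mortality = (m − L·e) / (1 − L·e)

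- L = 0.30: (0.15 − 0.0225) / (1 − 0.0225) = 0.1275 / 0.9775 = 13.0%
- L = 0.50: (0.15 − 0.0375) / (1 − 0.0375) = 0.1125 / 0.9625 = 11.7%
- L = 0.50, m = 0.10: 0.075 / 0.975 = 7.7%
- L = 0.50, m = 0.25: 0.1875 / 0.9375 = 20.0%

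**Step 2: whole cohort from implant.** In-hospital deaths enter under Appendix 2. With m = 0.15, true 1-year mortality is 0.24 + 0.76 × 0.15 = 35.4%.

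Apparent mortality = (0.354 − S·L·e) / (1 − S·L·e)

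- L = 0.30: (0.354 − 0.0171) / 0.9829 = 34.3%
- L = 0.50: (0.354 − 0.0285) / 0.9715 = 33.5%

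**Step 3: wider range.** Take 500 treated patients for illustration, so 380 are discharged alive. Let f be the fraction of a late entrant's post-discharge deaths that precede consent. Lost deaths = 380 × L × m × f, and apparent 1-year survival = 380(1 − m) / (500 − lost deaths).

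| m | L | f | Deaths lost | True survival | Apparent survival | Excess (points) |
|---|---|---|---|---|---|---|
| 0.10 | 0.10 | 0.25 | 1.0 | 68.4% | 68.5% | 0.1 |
| 0.20 | 0.25 | 0.50 | 9.5 | 60.8% | 62.0% | 1.2 |
| 0.30 | 0.50 | 1.00 | 57.0 | 53.2% | 60.0% | 6.8 |

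**Step 4: does the remedy recover the truth?** Use the step 1 case among discharged patients only, each at risk from consent. Survival to day 90 comes from those who consented before discharge: 1 − 0.075 = 0.925. After day 90 both groups are at risk: 1 − 0.075/0.925 = 0.919. The product is 0.925 × 0.919 = 0.85, so mortality is 15% for any L below 1. Multiplying by discharge survival gives 0.76 × 0.85 = 0.646, or 35.4% mortality from implant. This assumes that mail and pre-discharge entrants share the same hazard once both are under observation.

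**The case against.** The best counter-argument is that the effect is small where it matters. Mortality is counted from AMICS or implant, and most early deaths occur in hospital, where Appendix 2 captures them without mention of consent. Over the whole cohort the shift is 1 to 2 points under the step 2 assumptions. Mail is a fallback to an approach before discharge, so a 30% to 50% share may be high. The tracked survival metric is discharge survival, which this mechanism does not inflate. If survivors who refuse or do not reply are excluded while in-hospital deaths enter, discharge survival is understated: losing 5% to 30% of survivors would turn 76% into 75.1% to 68.9%. All of this stands and limits the size.

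A second objection concerns the remedy. If delayed entry is applied to the whole cohort from implant, the early risk sets hold almost only patients who die in hospital, because survivors consent near discharge. The resulting bias can exceed the one being corrected. That also stands, and it is why the analysis must be split at discharge.

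Several stronger readings are tempting but not supported:

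- That late entrants contribute no deaths. Someone consenting at day 40 cannot be a 30-day death but can be a 1-year death.
- That the retrospective route's bias is unlimited. The documents give no basis for sizing it, which is a different statement.
- That the damage could never be repaired. Signed consent forms may carry dates, and the consent pages are not available here.
- That pilot patients were entered. The pilot is described as concluded within its own retrospective registry, and nothing shows that its patients were carried over.
- That the registry is mislabelled as prospective. Research Procedures separates retrospective index data from prospective follow-up.

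**Conclusion.** The point holds for post-discharge mortality. As written, the entry rule loses deaths between discharge and mailed consent. It also admits entries after one year that are either survivors only or open to selection on a known outcome. This is a fault in the entry rule and the data forms. An analysis plan could correct it only if consent date and route were available, and the forms do not ask for them.

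On the mail route the bias is downward. Under the main assumptions it is 2.0 to 3.3 points among discharged patients and 1.1 to 1.9 points in the whole cohort. The wider range gives 0.1 to 6.8 points. On the retrospective route, 1-year mortality is 0% by construction if signed consent is required. If it is not, neither direction nor size can be derived from the documents. The change is worth making because it is cheap and the single arm gives no offsetting comparison.

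**What to change.** 1. Add to the CRF the date of consent or entry and the route: before discharge, mail, or retrospective after one year. Add date of death to the CRF and follow-up forms, since the analysis below needs it.
2. Report discharge survival on all eligible treated patients, including in-hospital deaths.
3. Estimate post-discharge mortality separately among those discharged alive, with each consented patient at risk only from the consent date (or discharge, if later). Multiply the two survival figures to obtain 30-day and 1-year survival from implant. For 30 days, count only in-hospital deaths up to day 30, because a later one is not a 30-day death.
4. Show retrospective entries after one year separately and keep them out of the headline estimate. State when the year starts and whether consent is needed.
5. Reconcile Research Procedures with Appendix 2 on whether index data need consent. Step 2 depends on the answer.
6. Add boxes to the Patient Exclusion Form for death before consent and for a form not returned.

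**Cost.** A few date and tick-box fields and a short paragraph of text. The headline follow-up estimate rests on somewhat fewer patients and has slightly wider intervals. Late entrants stay in the registry and clinical care is unaffected.
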